2. SYNOPSIS

Trial Title	Does the Corin Optimised Positioning System improve clinical outcome in total hip arthroplasty? A multi-centre, two-arm randomised controlled trial	
Internal ref. no. (or short title)	The HAPI Trial	
Trial Design	Single-blinded randomised controlled trial comparing best practice total hip arthroplasty (THA) surgical technique and templating with the best practice THA surgical technique plus Corin Optimised Positioning System (OPS) to guide templating. We will perform an internal pilot after 100 participants have been recruited. If analysis shows the trial is feasible, we will then progress onto the full study.	
Trial Participants	Male and female adults between 18 and 85 years of age, with a dysfunctional hip caused by osteoarthritis (OA), post traumatic OA, inflammatory arthropathy, avascular necrosis and congenital/developmental problems, randomly selected from the THA waiting list at each participating centre.	
Planned Sample Size	460 participants. 230 patients will receive best practice THA with conventional templating; the other 230 will receive best practice THA with Corin OPS to guide templating. Patients who drop out will not be replaced. The first 100 patients will constitute an internal pilot: results of the internal pilot will be used to repower the study. We anticipate the projected sample size of 460 may change by 5% either way.	
Treatment duration	2 years	
Follow up duration	1 year	
Planned Trial Period	3 years	
	Objectives	Outcome Measures
Primary	To compare the efficacy of the Corin OPS system to guide templating in THA with standard templating in THA in reducing dislocation	Dislocation rate and re-operation for dislocation rate
Secondary	1. To determine whether the Corin OPS System improves Harris hip score, patient reported outcome measures (PROMs), reduces hospital stay and normalises gait more effectively than conventional surgery	1. PROMs: 
• Oxford hip score (OHS)• iHOT33• HAGOS• Pain detect• EQ5D• UCLA score

	
2, To determine whether the Corin OPS System improves leg length discrepancy compared to conventional surgery
 
3, To quantify the cost of Corin OPS within the clinical pathway and perform a full health economic analysis following surgery
 
4, To determine the reproducibility of the Corin OPS templating technique at implanting the acetabular cup into the planned position. This will be performed in a subgroup of 50 patients randomly selected from the OPS arm to undergo a post-operative CT scan
 
5, To determine whether the Corin OPS System increases operation duration compared to conventional surgery
	
Harris hip score (HHS) Length of hospital stay Gait analysis Cost analysis
 
2, Leg length measurement
 
3, Cost
 
4, Post-operative position of prosthesis measured relative to planned position, based on pre- and post-operative CT scans
 
5, Operation duration

--	--	---

3. ABBREVIATIONS

AE	Adverse event
AR	Adverse reaction
CI	Chief Investigator
CRF	Case Report Form
CT	Computed Tomography
CTRG	Clinical Trials and Research Governance
DMC	Data Monitoring Committee
EQ-5D	Euro-Qol Group 5-Dimensions Questionnaire
GCP	Good Clinical Practice
GP	General Practitioner
HAGOS	Copenhagen Hip and Groin Outcome Score
HHS	Harris Hip Outcome
HRA	Health Research Authority
ICF	Informed Consent Form

ICH	International Conference on Harmonisation
iHOT33	International Hip Outcome Tool-33
NHS	National Health Service
NRES	National Research Ethics Service
OA	Osteoarthritis
OHS	Oxford Hip Score
OPS	Optimised Positioning System
PI	Principal Investigator
PIL	Participant/ Patient Information Leaflet
PROM	Patient Reported Outcome Measure
R&D	NHS Trust R&D Department
REC	Research Ethics Committee
SAE	Serious Adverse Event
SOP	Standard Operating Procedure
SUSAR	Suspected Unexpected Serious Adverse Reactions
THA	Total Hip Arthroplasty
TMF	Trial Master File
UCLA score	University of California, Los Angeles Activity Score

4. BACKGROUND AND RATIONALE

Osteoarthritis (OA) is the most common joint disease worldwide affecting an estimated 10% of males and 18% of females over 60 years of age¹. The resultant pain and loss of function can be debilitating and in developed countries represents a large socioeconomic burden, costing between 1% and 2.5% of gross domestic product, which currently stands at over £1.5 trillion². Total hip arthroplasty (THA) is an effective treatment for end-stage hip arthritis; however, demand for the procedure is growing rapidly, fuelled by an ageing population and the obesity epidemic³. In fact, rates of THA are predicted to rise 174% between 2005 and 2030⁴. The current commissioning environment in developed countries means that investment in iterative improvements of existing THA implant designs are unlikely to yield either significant benefits to patients or be supported by health funders. The two principle issues that concern surgeons and patients are the longevity of implants and the ability of new technologies to minimise complications such as dislocation and infection. The James-Lind Priorities Setting Partnership, an internationally recognised patient-driven organisation, has recently identified these pre-operative and intra-operative factors as targets for improving outcome following hip and knee replacement^{5,6}.

One of the largest costs to healthcare providers following THR is dislocation⁷. Although the dislocation rate reported in Joint Registries is between 1 and 3%^{8,9}, we know that this significantly underestimates the true problem, as the majority of dislocation events are managed with closed reduction and do not result in revision surgery¹⁰. It is estimated that dislocation is an order of magnitude more common than reported

in Registry data. Literature estimates indicate a true dislocation prevalence of 3 to 15%^{9,11,12}. The cost of dislocation is significant as the problem is often recurrent, resulting in multiple hospital admissions. The resulting average cost for each patient who suffers a THR dislocation is around £30,000⁷.

The factors that influence dislocation are poorly understood. Conventional surgical wisdom dictates that placing a cup in the Lewinneck 'safe zone' reduces both instability and wear¹³. A recent study of 9784 primary THAs, however, demonstrated that 58% of patients who suffered a dislocation had implants judged to be in a safe position¹⁴. This has led to suggestions that the idea of one generic 'safe zone' may be misleading^{14,15}; instead, there is a unique optimum position to place a cup in each patient undergoing THA, based on the unique and complex interaction of the spine and pelvis of the individual. Thus, in some patients, whilst the acetabular cup appears well positioned by conventional measures, pelvic tilt and spinal position mean that the cup is placed in a position of instability during some activities.

The Corin Optimised Positioning System (OPS) is a novel platform, designed to enable delivery of the prosthetic acetabular cup into an optimised position for every patient undergoing THA¹⁶. It comprises two stages: pre-operative planning and intra-operative guidance. Pre-operatively, patients undergo dynamic imaging (computed tomography scanning and X-ray films). The information gained about the relative movements of a patient's spine, pelvis and hips are used to create a personalized physiological profile. This enables calculation of the optimized acetabular cup orientation for each individual. A unique physical guide (which falls under the definition of a custom-made device in the Medical Device Directive) is then created for each patient to fit precisely into the acetabular fossa, for use intra-operatively. Intra-operatively, the Corin OPS uses laser alignment to aid the surgeon in aligning the acetabular cup in the calculated optimised orientation. One laser is affixed to an immovable pelvic screw; the other is attached to the reverse of the acetabular cup. The target orientation of the cup is achieved when the two lasers are aligned.

The aim of this trial is to assess the efficacy of the use of the Corin Optimised Positioning System in reducing post-operative hip dislocation in patients undergoing total hip arthroplasty by comparing it with current standard templating in total hip arthroplasty. All total hip implants/components used in the study will be produced by Corin for uniformity and are CE marked. There is currently no evidence that this novel approach to templating has an effect on dislocation rate. This project aims to provide evidence that this new technique can improve outcomes for patients and have the potential to reduce the need for complex, expensive revision surgery.

5. OBJECTIVES AND OUTCOME MEASURES

Objectives	Outcome Measures	Timepoint(s) of evaluation of this outcome measure (if applicable)

Primary Objective
 
To compare the efficacy of the Corin OPS system to guide templating in THA with standard templating in THA in reducing dislocation
	Dislocation rate and re-operation for dislocation rate	Pre-operatively, then at 3,6 and 12 months post-operatively

Secondary Objectives	
1, PROMs:
 
 • Oxford hip score (OHS) • iHOT33 • HAGOS • Pain detect • EQ5D • UCLA 
Harris hip score (HHS)
 
Length of hospital stay
 
Gait analysis
 
2, Measurement of leg lengths
 
3, Cost of inpatient stay for THA and cost of all patient care pertaining to their THA
 
4, Post-operative position of prosthesis measured relative to planned position, based on pre- and post-operative CT scans
 
5, Operation duration
	
1, PROMS and HHS recorded pre-operatively, then at 3, 6 and 12 months post-operatively. Gait analysis pre-operatively and at 12 months post-operatively (25 patients in each arm). Length of hospital stay will be recorded on discharge
 
2, X-rays and leg lengths will be assessed pre-operatively, then at 12 months post-operatively
 
3, Cost calculated 12 months post-operatively
 
4, CT scans pre-operatively and at 12 months post-operatively
 
5, Recorded at end of operation

1, To determine whether the Corin OPS System improves Harris hip score, patient reported outcome measures (PROMs), reduces hospital stay and normalises gait more effectively than conventional surgery
 
2, To determine whether the Corin OPS System improves leg length discrepancy compared to conventional surgery
 
3, To quantify the cost of Corin OPS within the clinical pathway and perform a full health economic analysis following surgery
 
4, To determine the reproducibility of the Corin OPS templating technique at implanting the acetabular cup into the planned position. This will be performed in a subgroup of 50 patients randomly selected from the OPS arm to undergo a post-operative CT scan
 
5, To determine whether the Corin OPS System increases operation duration compared to conventional surgery
		

6. TRIAL DESIGN

This will be a multi-centre, two-arm, single blind (participant blind), randomised controlled group superiority study. It will take place in the NHS hospital setting. Stratification will be performed for age and sex by means of a minimisation technique during randomisation for each subject entering the trial. There will be no limit on the number of sites and no limit on the number of recruits per site. The study site shall maintain a list of the participating sites and investigators separately to the protocol.

Arm 1

Best practice total hip arthroplasty with conventional templating

Arm 2

10/11/17

Protocol 1.2

Page 9 of 28

Does the Corin Optimised Positioning System improve clinical outcome in total hip replacement?

Chief Investigator: [name]

IRAS Project Number: 216084

Rec Reference Number: 17/SC/0506

Best practice total hip arthroplasty with Corin Optimised Positioning System to guide templating

In the study 230 participants will receive best practice THA with conventional templating; the other 230 will receive best practice THA with Corin OPS to guide templating. Any participant that withdraws from the study will not be replaced.

Initially we will perform an internal pilot study of 100 participants, with 50 participants in each arm. This will enable us to check feasibility of recruitment and to check our power calculation is correct. We anticipate recruitment to the pilot study will take six months, with an average of four participants recruited per week. Together the five centres currently recruited performed 3419 primary total hip replacements in 2015, an average of 66 per week⁸. Since participants in the two arms receive the same procedure, with the difference being in the technique used, with clear explanation of the trial to potential participants, we anticipate that approximately 50% of eligible patients that are approached will consent to take part in the trial. With this knowledge, we believe recruitment of initially four (rising to six) participants per week will be attainable. If the internal pilot study shows that completing the study is unfeasible, then the trial will be terminated following mutual agreement from both the Chief Investigator and the funder (Corin Limited). We anticipate recruitment to the full trial will take two years.

The expected duration of participant participation is 15 months. Following recruitment in outpatient clinics, participants will undergo baseline assessments, including imaging (CT scan and x-rays of pelvis) and clinical assessment. A subset of 50 participants will be randomly selected to also undergo gait analysis as part of the baseline assessments pre-operatively. All participants will then undergo THA surgery, which will likely entail an in-patient hospital stay of 1-7 days. Post-operative rehabilitation will be in line with the normal standard care for all participants. Post-operatively participants will make three additional visits to clinic at 3, 6 and 12 months, compared to routine follow up. At every visit, participants will complete the PROM questionnaires and undergo clinical assessment, as specified in section 5. Any dislocations or further surgeries will be recorded. All healthcare visits will be recorded, to enable cost analysis. At the 12 month post-operative visit participants will have standardised anteroposterior and lateral X-rays taken. At the 12-month visit, the subset of participants who were selected to undergo gait analysis pre-operatively will undergo repeat gait analysis. The subset of 50 patients who were randomly selected to undergo a second pelvic CT scan, will have this scan performed at the 12-month visit. Any patients in the study who do suffer a dislocation will be managed in line with the normal standard care. See sections 8.5 and 8.6 for more detail on visit schedule.

There will also be a third observational arm to the study. When patients are approached in clinic and offered entry into the randomised controlled trial, some patients may decline to take part. These patients will then be offered entry into the third observational arm of the study. This third study arm therefore will consist solely of patients who were approached in clinic but declined to be randomised into the clinical trial.

Patients in the third observational arm will continue in routine care as normal, and will not make any additional study visits. Their demographics will be collected and their pre- and post-operative Oxford hip scores and EQ-5D scores will be collected, as occurs in routine care. This third observational study arm will enable an assessment of whether the cohort who consented to undergo randomisation and enter the two randomised study arms are representative of all patients.

7. PARTICIPANT IDENTIFICATION

7.1. Trial Participants

Trial participants will be male and female adults between 18 and 85 years of age, with a diagnosis of hip OA, post-traumatic OA, inflammatory arthropathy, avascular necrosis, or congenital/developmental hip disease. Their disease is severe enough to warrant total hip arthroplasty (THA). Once recruitment begins, patients meeting the inclusion criteria will be identified at consultant-led outpatient and pre-operative assessment clinics at each participating centre. Patients will be approached during clinic appointments and offered entry into the trial.

7.2. Inclusion Criteria

- Participant is willing and able to give informed consent for participation in the trial
- Male or Female, aged 18 to 85 years at recruitment into trial
- Diagnosed with hip OA, post-traumatic OA, inflammatory arthropathy, avascular necrosis, or congenital or developmental hip disease, avascular necrosis of the hip
- Listed for total hip arthroplasty at one of participating centres
- Female participants of child bearing potential must be willing to ensure that they use effective contraception during the trial
- Participant is fit to undergo total hip arthroplasty based on consultant anaesthetist review
- In the Investigator's opinion, is able and willing to comply with all trial requirements
- Willing to allow his or her General Practitioner and consultant, if appropriate, to be notified of participation in the trial

7.3. Exclusion Criteria

The participant may not enter the trial if ANY of the following apply:

- Inability to provide informed consent
- Previous surgery to the ipsilateral hip
- Significant co-morbidities that would make follow up difficult or uncomfortable
- Scheduled elective surgery or other procedures requiring general anaesthesia during the trial
- Pregnancy

8. TRIAL PROCEDURES

[figure not shown]
8.1. Recruitment

Once recruitment begins, potential participants will be identified at consultant-led outpatient and pre-operative assessment clinics at each participating centre. During clinic appointments, orthopaedic surgeons will introduce the study to patients and refer them to a member of the study team, who will also be present in clinic, to discuss the study in detail and provide any further information requested. Patients will be asked to "opt-in" if they are provisionally interested in participating. If patients agree to "opt-in" they will be asked to sign the opt-in form and leave their contact details on a document detailing their agreement and permission to being contacted by a member of the research team to further discuss the study. Signing this document does not confer consent to participating in the study, simply to being contacted to further discuss the study. If potential participants do not wish to opt-in and are not interested in participating in the randomised study, they will be offered entry into the third observational study arm at this point.

After signing the "opt-in" document, potential participants will then be given a minimum of 48 hours to consider the study information and to discuss the study with their family and GP should they desire. Potential participants will then be contacted by telephone. At this time, any further questions will be addressed, and if the individual would like to participate in the study, a consent visit will be arranged for consenting. It is proposed that these appointments will occur within four weeks of the initial approach. If when contacted by telephone potential participants decline to take part in the randomised study, they will be offered entry into the third observational study arm.

At the consent appointment participants will meet with a member of the research team again to discuss the process and to discuss the study further. The surgeon may also attend this visit. It will be clearly stated that the participant is free to withdraw from the study at any time for any reason without prejudice to future care, and with no obligation to give the reason for withdrawal. The research nurse obtaining consent will be suitably qualified and experienced. A copy of the signed Informed Consent will be given to the participants and the original signed form will be retained at the study site.

After participants have consented to take part in the randomised study, randomisation will occur and the baseline assessment visit will be scheduled. For participants in the third observational arm of the study, they will continue in routine care as normal with no further study visits. Their demographic data and pre-and post-operative OHS and EQ5D, collected routinely, will be recorded for the study.

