8.4. Randomisation, blinding and code-breaking

Following written informed consent and confirmation of eligibility, all patients will be randomised into the study. Patients will be allocated a study number and will be randomised on a 1:1 basis to receive one of the two treatment options. During study recruitment, 50 participants (25 in each study arm) will be randomly selected to undergo gait analysis. At the end of study recruitment, 50 participants will be randomly selected from arm 2 (OPS arm) of the study cohort to have a second CT scan, which will be performed at 12-months post-operatively.

Randomisation will be performed using an automated computer-generated minimisation system through the Oxford Surgical Interventional Trials Unit to age (<40, ≥40 and <65, or ≥65), and gender. This process will occur centrally in Oxford and be overseen by the trial coordinator. Investigators at other sites will contact the site in Oxford to get each participant's randomisation allocation. Patients will be blinded as to which arm of the trial they have been allocated. The Oxford trial coordinator, the operating surgeon and the theatre staff will be unblinded and aware of which treatment arm the patient is in. The post-operative care team will remain blinded.

The Oxford trial coordinator will retain a full list of all recruited patients, their anonymous code number, and the treatment arm they have been allocated to. Trial coordinators at other sites and all operating surgeons will have access to a partial list, containing the same information on patients recruited at their own site only.

They will be the only people with access to this list. They will not have any role in collecting, reviewing, or interpreting post-operative data. Members of the research team who will be post-operatively assessing patients clinically, reviewing images or collecting and interpreting PROMs data will be blinded to patient allocation.

We do not anticipate a situation where code breaking will be required because the surgeons are not blinded to which arm the patients are in.

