8.5. Baseline Assessments

The follow assessments will be carried out at the baseline appointment:

Validated Patient Reported Outcome Measures (PROMs) Questionnaires:

Oxford hip score (OHS); International Hip Outcome Tool-33 (iHOT33); Hip and Groin Outcome Score (HAGOS); Pain Detect score; University of California, Los Angeles (UCLA) Activity Score; EuroQoL-5D score (EQ5D); Harris hip score (HHS)

CT scan:

CT imaging of pelvis

X-Ray:

Dynamic series of x-rays of pelvis and hip

Pregnancy test

Clinical assessment:

Examination of range of movement; examination of fixed flexion deformity; examination of leg length discrepancy

Subset of 50 participants (25 in each arm) will undergo gait analysis. These participants will be randomly selected from each study arm. Participants with comorbidities that significantly affect their gait will be excluded from gait analysis.

Assessors of all imaging, PROMs, and clinical assessment will be blinded to which arm of the trial patients were in.

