8.6. Summary of Visits

Routine clinical practice will take priority and the study timetable has been drawn up to allow the study procedures to fall within current surgical waiting times. Taking part in the study, therefore, will not delay or expedite treatment. Below is a summary of what will take place at each visit:

Visit 1: Consent visit

- Scheduled within 4-6 weeks of when potential participants are initially approached
- Consent form discussed and signed
- Following this visit, participants will be randomised into one of the two study arms
- If patients decline entry into the study, they will be offered entry into the 3rd observational arm of the study

Visit 2: Baseline assessment visit

- Scheduled for soon after consent visit
- Baseline assessments (detailed in section 8.5) completed

Visit 3: Gait Analysis Visit (subset of patients only)

- Scheduled for same day as or soon after baseline assessment visit (because scheduling CT scan and gait analysis on the same day may not be possible)

Visit 4: Study intervention

- Scheduled for 6-8 weeks after the baseline assessment (Thus patients will have a wait for surgery of approximately 3 months after entry into the study, which is in line with the current surgery waiting time in the participating centres.) Participants will undergo THA surgery in accordance with their randomisation allocation.
- Operative details to be collected:

- Date of surgery
- Randomisation group
- Name of consultant in charge of care
- Grade of lead surgeon
- Grade of assistant surgeons
- Operative side
- Duration of surgery
- Estimated blood loss
- Surgical approach
- ASA grade
- Use of systemic prophylactic therapy (antibacterial and anticoagulant)
- Anaesthesia type
- Acetabular and femoral bone quality
- Whether there was an attempt to correct leg length (if so, what amount attempted and achieved)
- Occurrence of per-operative complications
- Ease of reduction
- Acetabular grafting performed
- Femoral grafting performed
- Details of hip prosthetic components used – including information from device labels
- Other comments on operation

Visit 5: 3-month post-operative visit

- Completion of PROM questionnaires
- Clinical assessment (to include full examination of hip joint and assessment of leg length discrepancy)
- Recording of dislocations, further surgeries or adverse events
- Recording of details of any other healthcare usage by the participants (for cost analysis)

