9. DESCRIPTION OF PROCEDURES

THA will be performed under general anaesthesia or spinal anaesthesia. The surgical technique will be standardised across all sites. All surgeons operating within the trial perform in excess of 60 hip arthroplasties annually. THA will be performed via anterior, antero-lateral, lateral or posterior approach. The study will use the Corin Trinity shell system for the acetabular system. The study will use all compatible Corin stem implants (MiniHip, TriFit, MetaFix and TaperFit) for the stem implant. All head and stem sizes will be included in the trial. All implants will be supplied by Corin Ltd. Pre-operatively all patients (both arms) will undergo dynamic imaging (computer tomography scanning and X-ray films) of their pelvis and hips.

Arm 1: Best practice total hip arthroplasty (THA) with conventional templating

An antero-posterior view radiograph of the pelvis (with legs positioned in 15° internal rotation) and a lateral view radiograph of the hip are required for conventional templating. The radiographs will be examined pre-operatively and appropriately sized cup and stem implants selected for each patient. Intra-operatively, the surgeon may select a different sized implant to that predicted by templating if clinically appropriate.

Arm 2: Best practice total hip arthroplasty (THA) with Corin OPS to guide templating

Patients in the intervention arm will undergo an identical total hip arthroplasty operation. The difference will be the templating procedure used to accurately align the acetabular cup.

The pre-operative dynamic imaging of patients in the OPS arm will be used to calculate the personalised target orientation of the acetabular cup in each patient. A unique physical guide is then created for each patient, which facilitates the accurate positioning of the prosthetic acetabular cup. The guide is a model that fits precisely into the acetabular fossa.

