9.1. Discontinuation/Withdrawal of Participants from Trial Treatment

Each participant has the right to withdraw from the trial at any time. In addition, the Investigator may discontinue a participant from the trial at any time if the Investigator considers it necessary for any reason including:

- Pregnancy
- Ineligibility (either arising during the trial or retrospectively having been overlooked at screening)
- Significant protocol deviation
- Significant non-compliance with trial requirements
- An adverse event which requires revision surgery
- Withdrawal of Consent
- Loss to follow up

The reason for withdrawal will be recorded in the CRF.

If the participant is withdrawn due to an adverse event, the Investigator will arrange for follow-up visits or telephone calls until the adverse event has resolved or stabilised.

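### Patients are randomised before the baseline visit, which holds the only pregnancy test and all baseline scores, although section 8.4 requires eligibility to be confirmed before randomisation

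*Combined protocol and SAP*

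**What the plan says.** **Order of events.** Section 8.1 states that, once consent is given, "randomisation will occur and the baseline assessment visit will be scheduled". Section 8.6 agrees. Under Visit 1, the consent visit, it says "Following this visit, participants will be randomised into one of the two study arms", and Visit 2, the baseline visit, is "Scheduled for soon after consent visit".

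**Eligibility.** Section 8.4 sets the condition: "Following written informed consent and confirmation of eligibility, all patients will be randomised into the study". Section 7.3 lists pregnancy among the exclusions. Appendix B puts the eligibility assessment at the consent visit.

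**Content of the baseline visit.** Section 8.5 lists "Pregnancy test" there, with six PROM instruments, the Harris hip score, range of movement, fixed flexion deformity, leg length discrepancy, pelvic CT and dynamic X-rays. No earlier visit includes a pregnancy test, and Appendix B has no row for one.

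**Content of the consent visit.** Date of birth, gender, BMI, smoking status, medical history and medication are collected after consent as part of screening (section 8.2). Appendix B places demographics and history at the consent visit.

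**After randomisation.** Section 9.1 lets the investigator discontinue a participant for pregnancy or for ineligibility discovered late. Section 6 rules out replacement. Sections 11.2 and 11.6 keep every randomised participant in the analysis.

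**The concern.** One exclusion criterion is tested only after the patient has been allocated. For a woman of child-bearing potential, the condition in section 8.4 cannot be met by any check the protocol lists. If the baseline test is positive, or if any patient leaves before that visit, the trial has a randomised participant who may have no baseline scores, no trial surgery and no 12-month outcome, and who still belongs in the intention-to-treat set.

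The second issue is the status of the Visit 2 measurements. A score taken before allocation cannot be influenced by allocation. A score taken afterwards is protected only as far as blinding holds. At that point operating surgeons and site coordinators have access to the allocation list. Section 8.4 bars them from handling post-operative data and does not mention baseline data.

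**Working it through.** **1. The order, set side by side**

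| Step | Where placed | Source |
|---|---|---|
| Eligibility assessment | Consent visit | Appendix B |
| Demographics, history, medication | Screening after consent | 8.2, Appendix B |
| Randomisation | After Visit 1, when Visit 2 is being scheduled | 8.1, 8.6 |
| Pregnancy test | Visit 2 | 8.5 only |
| PROMs, HHS, examination, CT, X-rays | Visit 2 | 8.5, Appendix B |

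Section 8.5 supports this reading. It draws the gait subset from each study arm and describes baseline assessors as blinded to arm, and both presuppose that arms already exist at baseline. The one-year limit between screening and randomisation in section 8.2 does not move the baseline visit ahead of allocation.

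**2. Is early allocation needed?** Section 9 says "Pre-operatively all patients (both arms) will undergo dynamic imaging", so imaging does not depend on the arm. The OPS guide is made from that imaging, so work on it cannot begin before Visit 2 under either order. Surgery is timed at 6-8 weeks from the baseline assessment (section 8.6). Allocating at the end of Visit 2 leaves that interval as it is.

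**3. The plan's sample size, reproduced.** Inputs from sections 11.1 and 11.3: p1 = 0.05, p2 = 0.005, two-sided alpha 0.05, power 0.80, dropout 10%. With mean proportion p = 0.0275:

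n per arm = [1.960 × √(2p(1−p)) + 0.842 × √(p1(1−p1) + p2(1−p2))]² / (p1−p2)²

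= [1.960 × 0.2313 + 0.842 × 0.2291]² / 0.045² ≈ 206.1, rounded up to 207.

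Total 2 × 207 = 414, and 414 / 0.9 = 460. Both figures match the plan. Power at 207 per arm is 0.802.

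**4. Size of the loss.** The documents give no rate for patients lost or found ineligible between consent and baseline, so the rates e below are assumptions. They are taken on top of the 10% dropout, which is the unfavourable case. Evaluable = 460 × 0.9 × (1−e). Number needed to keep 414 evaluable = 414 / (0.9 × (1−e)), rounded up.

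| Extra loss e | e × 460 | Evaluable | Power | N to keep 414 |
|---|---|---|---|---|
| 0 | 0 | 414 | 0.802 | 460 |
| 0.5% | 2.3 | 412 | 0.800 | 463 |
| 1% | 4.6 | 410 | 0.798 | 465 |
| 2% | 9.2 | 406 | 0.794 | 470 |
| 5% | 23.0 | 393 | 0.781 | 485 |

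If these losses fall within the 10% allowance, power does not change.

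**The case against.** Five points can be made for the plan, and most of them limit how far the concern reaches.

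- **Baseline covariates.** A reader might infer that all baseline covariates are measured after allocation. They are not. Age, sex, BMI, smoking, history and medication are collected at the consent visit, and the minimisation factors (age band and gender) must be known before allocation. Only Visit 2 items come later.
- **Bias.** A reader might infer that the adjusted analysis is contaminated. Section 11.2 names no adjustment covariates, so nothing shows that the Visit 2 scores enter the primary model. Patients are to be blinded (section 8.4), and so are assessors of imaging, PROMs and clinical examination (section 8.5). Bias would need a failure of blinding, which the documents do not describe.
- **Intention to treat.** A reader might infer that the order of visits creates a conflict between withdrawal under section 9.1 and analysis as randomised. That tension exists wherever randomisation sits, because ineligibility or pregnancy can also arise later. In addition, discontinuing a participant does not in itself prevent her from being analysed as randomised. Reordering reduces the number of such cases without settling the question.
- **Scale.** The baseline visit comes soon after consent, and the 6-8 weeks before surgery would still follow allocation. Reordering removes only losses in the short gap between the two visits, and the effect on power is small.
- **Logistics.** Allocating first allows the 25-per-arm gait subset to be drawn and booked ahead in a laboratory with limited capacity.

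It could also be argued that eligibility is confirmed from the history at the consent visit and that the later test is only a safety check. The protocol does not say so. The test at Visit 2 is the only pregnancy check it lists. The contradiction over eligibility therefore stands, as does the fact that Visit 2 measures follow allocation.

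**Conclusion.** The concern holds in a limited form. Sections 8.1 and 8.6 place randomisation before the only test for one exclusion criterion, against section 8.4, and Appendix B declares eligibility assessed before that test. Patients found ineligible or lost between consent and baseline are randomised, not replaced and counted in the intention-to-treat set, possibly without baseline scores. Visit 2 measures are taken after allocation and depend on the planned blinding of patients and assessors.

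The effect on power is small: from 0.802 to 0.794 at an assumed 2% extra loss. That range has no source in the documents, and the conclusion does not depend on it. The conclusion rests on the order of visits as written and on section 8.5 being the only place where a pregnancy test appears. The documents do not support a claim of biased baseline data or of a material shortfall in sample size.

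**What to change.** Amend sections 8.1, 8.4, 8.6 and Appendix B together so that central randomisation takes place at the end of the baseline visit. By then eligibility, including the pregnancy test, should be confirmed, and the baseline scores, examination and imaging should be complete. Add a pregnancy-test row to Appendix B and align its eligibility row with the new order. Draw the gait subset at the same point.

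**Cost.** One step moves. No visit is added, the sample size stays at 460, and the 6-8 weeks from baseline to surgery are unchanged. The downside is practical: the allocation request to the Oxford coordinating site must be handled at that visit, as must the gait booking where gait analysis falls on the same day. Section 8.6 already allows gait analysis soon after baseline, which eases this.
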